 - Preterm birth before 30 weeks: rate of delivery before 29+6 weeks
 - Preterm birth before 28 weeks: rate of delivery before 27+6 weeks
 - Birth weight: median weight (g) of the newborns at birth
 - Fetal or neonatal death: rate of intrauterine demise or neonatal death during the first 24 hours
 - Neonatal morbidity: rate of major adverse neonatal outcomes before discharge from the hospital
 - Intraventricular Haemorrhage (IVH): grades III-IV
 - Retinopathy of prematurity
 - Respiratory Distress Syndrome (RDS): grades II-IV,
 - Need for ventilation > 72 h
 - Necrotising enterocolitis
 - Proven or suspected sepsis, antibiotics (>5 days)
 - Need (Duration in days) for neonatal special care (NICU)
 - Harm from intervention
- Mother:
- Maternal death
 - Significant maternal adverse events (rate):
 - Heavy bleeding: bleeding that requires a medical intervention
 - Cervical tear: cervical rupture due to the pessary placement
 - Uterine rupture: rupture of the uterus due to contractions or surgery
 - Physical or psychological intolerance to pessary: discomfort or pain due to the pessary that makes daily life uncomfortable (number of cases)
 - Rupture of membranes before 32 weeks: rate of—rupture of amniotic membranes before 31+6 weeks
 - Infection/inflammation
 - Hospitalisation for threatened preterm labour before 32 weeks: requirement of hospitalisation due to preterm contractions that need medical treatment to try to stop them before 31+6 weeks (rate)
 - Mean hospital stay duration: number of days of admittance at the hospital
 - Use of tocolytic treatment: Type of tocolytic, days of treatment, dose

4.2. Description of the trial design.

Open Multicentre International Collaborative Randomized Controlled Trial, in parallel groups, based on intention-to-treat analysis comparing the placement of a prophylactic cervical pessary with usual management in singleton pregnancies at high-risk of PTB due to a history of at least one previous preterm delivery before 34+0 weeks and/or a history of previous cervical surgery.

4.3. Flowchart.

Confidential

4.4. Description of the medical device and the treatment regimen.

The cervical pessary is a vaginal device (silicone ring) that is used to treat pregnant women for preventing spontaneous preterm birth. This device can be easily placed around the uterine cervix without pain (see annex I).

Confidential

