(2) The primary outcome will be evaluated 3 years after the last woman enrolled in this study has delivered her neonate.

Confidential

A descriptive analysis by preterm birth will be carried out calculating means and medians for quantitative variables and proportions with 95% confidence intervals for categorical variables.

Additionally we will perform an explorative subgroup analysis of the study collective comparing the efficacy of the cervical pessary treatment in women with a normal cervical length at 12 -16 weeks of gestation and in women who have developed a cervical shortening (< 25 mm) as an additional risk factor.

For the primary endpoint we expect to have a drop out rate of up to 25% due to the long follow-up time (3 years) of the study; but we do not expect to have lost data for the secondary endpoints because for these parameters the study has a short follow-up time till time to birth only.

An interim analysis shall be conducted on key safety parameters after birth of 150 neonates: the following safety endpoints will be assessed by a one-sided test with $\alpha=1\%$

- on level of the neonates:

rate of preterm birth, time to birth, birth weight, death, neonatal morbidity, harm of intervention

- and on the maternal level:

rate of hospitalisation for threatened preterm labour < 32 weeks, rate of P_{RoM} <32 weeks, rate of infection / inflammation, rate of physical or psychological intolerance to pessary, rate of SAR/SAE, death.

The trial will be terminated as negative if a disadvantage for the pessary-treatment can be found in one of these tests. To guarantee a high safety level the significance level is chosen more conservatively than in a Bonferroni correction. All analysis will be carried out with SPSS® version 19.0 or later (IBM Company SPSS Inc.

Headquarters, Chicago, Illinois, USA) and R version 3.2.3 or later (R Foundation for Statistical Computing, Vienna, Austria).

Primary Outcome	Statistical Test
Children`s Long-Term Survival without Neurodevelopmental Disability (3-Years-follow up)	Chi-Square test
Secondary Outcome	Statistical Test
Birth before 34 Weeks of Gestation	Chi-Square test or Fisher test
Time to Birth	Cox regression
Birthweight	t-test or Wilcoxon-Mann-Whitney test
Fetal / Neonatal Death	Chi-Square test or Fisher test
Neonatal Morbidity	Chi-Square test or Fisher test
Need for Hospitalization	Chi-Square test or Fisher test
Days of Hospitalization	t-test or Wilcoxon-Mann-Whitney test

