Maternal Adverse Events	Chi-Square test or Fisher test
Pessary Intolerance	Chi-Square test or Fisher test
Vaginal Infections	Chi-Square test or Fisher test

9.2. Expected number of subjects to be included.

For sample size calculation, we assume a combined event rate for the primary outcome (long-term survival without neurodevelopmental disability at 3 years of follow up) of 8% for the pessary group (see van't Hooft, Pro Twin Trial²⁸) and an event rate of 20% for the control group. Group sample size of 121 in both groups achieve 80% power to detect this difference using a two-sided chi-square test with significance level $\alpha=5\%$. To account for a drop out rate around 15%, sample size of 155 in each group, overall n=310 women will be recruited.

9.3. Criteria for termination of the trial.

A non-justified case of maternal death (temporary stop until complete evaluation of the case by an external committee).

9.4. Selection of subjects to be included in each analysis.

The analysis will include all the subjects that have been randomised.

10. Direct Access to Data Source

Direct access will be granted to the authorized monitor, host institution and the regulatory authorities to permit trial-related monitoring, audits and inspections.

11. Quality and Control Assurance

Main investigator and collaborators: In order to ensure the Quality of the data they will provide instructions and training to the sites involved in the trial; review the CRF data; and detail of any other steps taken to ensure quality of research.

The main investigator will sign the study protocol and the “investigator’s commitment; he will apply for the Ethics Committee and the Director’s approval; and he will review the final report of the study.

The collaborators will assess patient’s eligibility, they will inform the patients and ask for the informed consent; and they will be responsible of the CRF and obtaining and registering all data.

Monitor: he will perform regular monitoring according to ICH GCP. Data will be evaluated for compliance with the protocol and accuracy in relation to source documents. Monitors will verify that the clinical trial is conducted and data are generated, documented and reported in compliance with the protocol, GCP and the applicable and local regulatory requirements.

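### Neonatal morbidity and NICU days give death no place, so a pessary that turns fetal losses into live preterm births can look worse on both, and morbidity alone can end the trial at the interim

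*Combined protocol and SAP*

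**What the plan says.** Section 4.1.2 lists "Neonatal morbidity: rate of major adverse neonatal outcomes before discharge from the hospital". The conditions under it are severe intraventricular haemorrhage, retinopathy, respiratory distress syndrome, prolonged ventilation, necrotising enterocolitis and sepsis; death is not among them. The next item is "Need (Duration in days) for neonatal special care (NICU"), again without a rule for a fetus or baby that dies.

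Death is a separate secondary outcome: "Fetal or neonatal death: rate of intrauterine demise or neonatal death during the first 24 hours". A baby who dies in hospital after 24 hours falls outside that definition, and is a morbidity case only if one of the listed conditions was recorded.

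Section 5.1 sets entry at 12+0 to 16+0 weeks. Section 9.4 says "The analysis will include all the subjects that have been randomised", but no denominator is given for neonatal endpoints when a pregnancy is lost.

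On the interim, section 9.1 says "An interim analysis shall be conducted on key safety parameters after birth of 150 neonates" and "the following safety endpoints will be assessed by a one-sided test with" a significance level of 1%. The neonatal list is "rate of preterm birth, time to birth, birth weight, death, neonatal morbidity, harm of intervention", so death and morbidity are tested separately and NICU days is absent. The consequence is: "The trial will be terminated as negative if a disadvantage for the pessary-treatment can be found in one of these tests".

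**The concern.** A pregnancy lost at 20 weeks cannot show any listed morbidity and uses no NICU days. If it stays in the denominator it counts as a good result; if it is dropped, the control arm is left with a healthier selection of babies. Had the pessary prolonged the same pregnancy to a very preterm live birth, that baby would probably be morbid with a long stay. Both endpoints then move against the arm with better survival.

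For NICU days the cost is a misleading secondary comparison. For morbidity it is larger: one adverse test ends the trial as negative, nothing in the rule lets a better death result offset it, and the primary outcome, which does count death as failure, is read only three years after the last birth.

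**Working it through.** **The plan's own figures.** The documents give no expected rate, sample size or power for neonatal morbidity or NICU days, so there is nothing to reproduce on this point. The rates below are assumptions.

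**Inputs from the documents.** Interim at 150 neonates, taken as 75 per arm under equal allocation; one-sided 1% per test; chi-square or Fisher test for morbidity (table in section 9.1).

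**Assumed inputs (central value, range).**
- Morbidity among babies live-born under either arm, m = 10% (5–15%).
- Pregnancies lost under control but live under pessary, R = 5% (3–10%).
- Morbidity among those rescued babies, q = 80% (50–100%).
- Lost under either arm, L = 2%.
- No other effect of the pessary.

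Live under either arm: A = 1 − L − R = 93%.

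**Rates, central case.**
- All randomised: control A·m = 0.93 × 0.10 = 9.3%; pessary A·m + R·q = 9.3% + 0.05 × 0.80 = 13.3%.
- Live births only: control 10.0%; pessary 0.133/0.98 = 13.6%.
- Death or morbidity, all randomised: control 2% + 5% + 9.3% = 16.3%; pessary 2% + 13.3% = 15.3%.

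Morbidity points against the pessary with either denominator. The composite points in its favour.

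**When the interim test stops the trial.** With x and y cases in 75 each and p̄ = (x + y)/150, the test stops if z = [(x − y)/75] / √[p̄(1 − p̄)·2/75] exceeds 2.326. For 14 v 4: p̄ = 0.12, z = 0.1333/0.0531 = 2.51, stop. For 13 v 4: z = 0.1200/0.0518 = 2.32, no stop. Fisher's test needs 15 v 4.

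**Chance that this test alone stops the trial** (binomial probabilities summed over all stopping pairs):

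| Case | Chi-square | Fisher |
|---|---|---|
| Morbidity, all randomised, 13.3% v 9.3% | 5.3% | 3.4% |
| Morbidity, live births (74 v 70), 13.6% v 10.0% | 4.5% | 2.5% |
| No effect, 9.3% in both arms | 0.9% | – |
| Death or morbidity, 15.3% v 16.3% | 0.6% | – |

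Over the assumed ranges (36 combinations, chi-square), the morbidity stop chance runs from 1.8% (m = 15%, R = 3%, q = 50%) to 40.7% (m = 5%, R = 10%, q = 100%) over all randomised, and from 1.5% to 32.5% over live births. For the composite it runs from 0.06% to 1.0%. Morbidity is higher on pessary in all 36; the composite is equal or lower in all 36.

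**What would cancel it.** The relative fall in morbidity needed among the other babies is R·q/(A·m) = 0.04/0.093 = 43% over all randomised. Over live births, their morbidity would have to be (0.98 × 0.10 − 0.04)/0.93 = 6.2%, a fall of 38%. A larger fall reverses the direction.

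**NICU days.** With losses entered as zero and an assumed 60-day stay per rescued baby, the pessary mean rises by 0.05 × 60 = 3.0 days per randomised woman. The range is 0.03 × 30 = 0.9 to 0.10 × 90 = 9.0 days.

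**Cost of testing only the composite at the interim.** Assume 9% deaths in both arms and a true morbidity harm of 25% v 10% among the rest. Over all randomised, morbidity is 0.91 × 25% = 22.8% v 0.91 × 10% = 9.1%, detected with probability 49% at 75 per arm. The composite is 31.8% v 18.1%, detected with probability 35%.

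**The case against.** The strongest reply is that the trial does not ignore death. It is a secondary outcome, a separate interim endpoint and a failure in the primary outcome, and reporting death and morbidity side by side is common practice. That stands, and it limits the point to how these two endpoints are defined and tested.

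Four stronger readings are tempting and are not supported:

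- *That the pessary will look harmful.* The direction is certain only if rescue is its sole effect. The device is meant to reduce preterm birth generally, and less morbidity among the other babies could cancel or reverse the artefact.
- *That every early death scores as free of morbidity.* The list includes respiratory distress, intraventricular haemorrhage and sepsis, any of which a baby dying on day 1 may already have. The argument holds cleanly only for fetal losses.
- *That NICU days can stop the trial.* It is not on the interim list.
- *That the composite should simply replace morbidity in the interim test.* That would weaken detection of a real morbidity harm, as the 49% v 35% comparison shows.

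It is also fair to say that part of the weight comes from the rule that any one adverse test ends the trial, which is a separate matter. But that is the rule morbidity falls under, and the rule has no provision for reading morbidity together with survival.

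**Conclusion.** The point holds in a conditional form. Neither endpoint counts death as a bad outcome or states its denominator after a loss, so both can be biased against the arm with better survival. In the central assumed case, the chance that morbidity alone wrongly ends the trial rises from 0.9% to about 5% by chi-square (3.4% by Fisher). The artefact therefore usually stays short of the boundary, and the 40.7% upper end needs extreme inputs. All these sizes rest on assumed rates of morbidity and rescue and on no other pessary effect; the documents supply none of them. NICU days affects only the secondary analysis. This is a worthwhile, low-cost improvement; it does not undermine the primary analysis.

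**What to change.** - **Sections 4.1.2 and 9.1, morbidity.** Add fetal death, death before discharge or major neonatal morbidity as the comparative analysis, with all randomised pregnancies as the denominator. Show death and each morbidity component beside it, and state the denominator for each.
- **Sections 4.1.2 and 9.1, NICU days.** Compare by a Wilcoxon test in which fetal and in-hospital deaths take the worst rank. The test table has no NICU row; its hospital-days row offers a t-test or Wilcoxon test and may mean the mother's stay, so a row should be added.
- **Section 9.1, interim.** Keep the morbidity test, but give the data monitoring committee the composite and the deaths by arm with it. Amend the stopping sentence so that an adverse morbidity result is read together with survival before the trial is ended as negative.

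The cost is mainly wording. The composite mixes outcomes of different weight and is less sensitive to a pure morbidity harm, which is why the components and the separate interim morbidity test should stay. The date of any death up to discharge must be captured; the neonatal death outcome now stops at 24 hours, and the documents do not show whether the case report form records later deaths.

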Every center will receive a password and a username in order to access the database for recruitment, randomization and documentation of patient data. Hereby, a personal identification number will be assigned for every patient. Patient names will not appear in the databases.

This database will be supervised and coordinated by PD [name], Bürgerhospital Frankfurt/M. (Webmaster).

4.8. Identification of data to be collected in the case report files (CRF) that should be considered as data source.

Data will be collected in E-CRF, provided by >[name] Wissenschaft, Berlin< on study software "Castor".

4.9. Definition of what is considered to be the end of the study.

The study will be finished after the 3 year-follow up examination of the surviving children focusing on neurodevelopmental disabilities.

5. Selection and withdrawal of subjects

5.1. Inclusion criteria.

- Women with a singleton pregnancy and a history of at least one previous preterm delivery before 34+0 weeks and/or a history of previous cervical surgery
- 12+0 -16+0 weeks of gestation
- Minimal age of 18 years
- Informed consent signature

5.2. Exclusion criteria.

- Major fetal abnormalities (requiring surgery or leading to infant death or severe handicap)
- Cerclage prior to randomisation
- Uterine malformation
- Placenta previa totalis
- Active vaginal bleeding at the moment of randomization
- Spontaneous rupture of membranes at the time of randomization
- Silicone allergy
- Painful regular uterine contractions
- Current participation in another RCT

5.3. Withdrawal criteria.

If a participant may voluntarily withdraw from treatment or if it is necessary to remove the pessary due to the conditions described before, the patients will be followed as usual until delivery (intention-to-treat analysis).

Replacement of patients is not applicable in this trial.

5.4. Rescue treatment criteria.

Regarding the control group, a McDonald cerclage may be indicated if there is a cervical shortening below 25 mm during the follow-up scans according to the current guidelines and expert recommendations¹¹.

6. Treatment of Subjects

6.1. Treatments to be administered.

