The pessary will be inserted during a preventive examination in pregnancy in the examination room. This procedure does not need anaesthesia and it does not need to be done in a surgery room. After the insertion of the pessary the correct fit of the pessary is verified by transvaginal ultrasound and in case it does not fit perfectly, it can easily be adjusted. In the control-group the cervical length of the women will be evaluated by transvaginal ultrasound scan: if a cervical shortening below 25 mm is

Confidential

detected a cervical cerclage will be placed. The pessary or cerclage will be removed at 37+0 weeks of gestation, or before if any unexpected event occurs (see 4.6). After insertion of the pessary the obstetrical management during the pregnancy will be usual management. Further surveillance of the pregnancy will not be influenced by the participation on the study.

7. Efficacy assessment

7.1. Specification of efficacy parameters: Primary and secondary endpoints.

This study aims to investigate the benefit of a prophylactic cervical pessary treatment in women at high risk of PTB due to a history of at least one previous preterm delivery before 34+0 weeks and/or a history of previous cervical surgery on the perinatal outcome and on the children's long-term survival without neurodevelopmental disability.

The effect of the pessary treatment will be assessed in women independent of the cervical length at 12 -16 weeks of gestation compared to standard care treatment.

7.2. Methods and timing to assess records and analyze the efficacy parameters.

The pregnant women will be assessed according to usual obstetrical management in a high-risk pregnancy.

	Regular Preventive Exam	Serial CL measurements after randomization	Regular Preventive Exam 37 WoG	Postnatal evaluation	3 years follow up (corrected age)
Study procedure	study inclusion 12+0-16+0 WoG				
Informed consent	x				
randomisation	x				
Control-group		x			
Pessary/cerclage placement	Pessary-Group: Pessary at enrollment	Control-Group: Cerclage when CL \leq 25mm			
Pessary/cerclage removal	WoG 37+0		x		
physical exams					
Abdominal US	x	x	x		
Vaginal US		x			
pH-Value	pH < 4,4	pH < 4,4			
Neonatal examination				x	
Ages & Stages test					x
Exam at paediatrician					x

8. Assessment of Safety

8.1. Procedures to record and report adverse events.

Confidential

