If a serious and unexpected adverse effect occurs during pessary treatment, it will be notified to the study Sponsor. The Department of Obstetrics and Gynecology of the Sponsor will fill the side effects document to notify it to the *Landesärztekammer Hessen*.

The patient affected by the adverse effect will be followed more intensively during the first days and if nothing else occurs, she will return to the standard control.

8.2. Definitions.

Adverse Event (AE): Any untoward medical occurrence in a patient or clinical investigation participants administered a medicinal product, which does not necessarily have to have a causal relationship with this treatment (the study medication). An AE can therefore be any unfavourable and unintended sign (including an abnormal laboratory finding), symptom or disease temporally associated with the use of the study medication/procedure, whether or not considered related to the study medication.

Adverse Reaction (AR): All untoward and unintended responses to a medicinal product related to any dose. The phrase "responses to a medicinal product" means that a causal relationship between a study medication and an AE is at least a reasonable possibility, i.e., the relationship cannot be ruled out.

All cases judged by either the reporting medically qualified professional or the sponsor as having a reasonable suspected causal relationship to the study medication / procedure qualify as adverse reactions.

Serious Adverse Event (SAE): A serious adverse event is any untoward medical occurrence that at any dose: Results in death; is life-threatening, NOTE: The term "life-threatening" in the definition of "serious" refers to an event in which the participant was at risk of death at the time of the event; it does not refer to an event which hypothetically might have caused death if it were more severe; Requires inpatient hospitalization or prolongation of existing hospitalization; Results in persistent or significant disability/incapacity, or is a congenital anomaly/birth defect.

Other important medical events: Other events that may not result in death, are not life threatening, or do not require hospitalization, may be considered a serious adverse event when, based upon appropriate medical judgment, the event may jeopardize the patient and may require medical or surgical intervention to prevent one of the outcomes listed above.

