It will be left to the investigator's clinical judgment whether or not an AE is of sufficient severity to require the participant's removal from treatment. A participant may also voluntarily withdraw from treatment due to what he or she perceives as an intolerable AE. If either of these occurs, the participant must undergo an end of study assessment and be given appropriate care under medical supervision until symptoms cease or the condition becomes stable.

A medically qualified investigator will assess the relationship of AEs to the study medication.

All SAEs must be reported to the main investigator. He will perform an initial check of the report, request any additional information, and he will notify it to the Ethics Committee. All SAE information will be recorded. It may be appropriate that some SAEs do not require immediate reporting but this must be justified. Justification might be determined, for example, by admission to hospital, or prolongation of hospitalization, where this is to be expected in the underlying disease or condition.

All adverse events (AE) life-threatening or resulting in death will be notified within 24 hours. All AE that are not life-threatening will be notified within 15 days. The rest of AE will be recorded and analyzed at the end of the study.

9. Statistics

9.1. Description of statistical methods.

A descriptive analysis by preterm birth will be carried out calculating means and medians for quantitative variables and proportions for categorical variables.

The primary statistical aim is to compare the primary combined outcome "long-term survival without neuro-developmental disability at 3 years follow up" between the two treatment groups with a two-sided chi-square test. In general, statistical comparisons will be two-sided and use appropriate tests according to the scale of the outcome. A multivariate logistic regression will be fitted to control for possible confounders. Relative risks and 95% confidence interval as well as adjusted odds ratios will be calculated for the binary outcomes. Statistical significance will be accepted in all cases with a $p \leq 0.05$.

The main statistical evaluation will be performed at two time points.

(1) The complete data set for the secondary endpoints will be available after the last women enrolled in this study has delivered her neonate, so the analysis of these outcome parameter will be done right after this event.

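### Sections 5.3 and 8.3 do not carry women who stop treatment through to the 3-year primary outcome, no handling or sensitivity analysis is stated for up to 25% missing primary outcomes, and the dropout figure differs between sections

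*Combined protocol and SAP*

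**What the plan says.** **Follow-up after stopping treatment.** For women who withdraw from treatment or have the pessary removed early, section 5.3 says "the patients will be followed as usual until delivery (intention-to-treat analysis". For those whose treatment stops because of an adverse event, section 8.3 says "If either of these occurs, the participant must undergo an end of study assessment". That assessment is not defined in 8.3 and has no column in the 7.2 schedule.

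Other sections set the 3-year endpoint without any condition on treatment. Section 4.9: "The study will be finished after the 3 year-follow up examination of the surviving children". The 7.2 schedule has a column for "3 years follow up (corrected age". Section 9.1 times the primary analysis 3 years after the last delivery. Section 9.4: "The analysis will include all the subjects that have been randomised".

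**Missing primary outcomes.** Section 9.1 says of the primary endpoint that "we expect to have a drop out rate of up to 25% due to the long follow-up time", and expects no lost data for the birth outcomes. The named primary test is a two-sided chi-square. Sections 9.1 to 9.4 state no rule for a child without a 3-year outcome and no sensitivity analysis. The logistic regression in 9.1 is there for confounders, and the subgroup analysis concerns cervical length.

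**Dropout figure.** The synopsis says around 25%, 9.1 up to 25%, and 9.2 around 15%. The synopsis and 9.2 both give 121 evaluable and 155 recruited per arm.

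**The concern.** The label intention-to-treat in 5.3 is attached to follow-up that stops at delivery, while the primary outcome is measured 3 years later. A site reading 5.3 or 8.3 literally could close a woman's participation and never arrange the child's 3-year assessment. Such loss may not be random, because the early-removal reasons in 4.6 (bleeding, contractions, membrane rupture) are related to prognosis. It may also be uneven. Every pessary-arm woman has a device from enrolment, while controls receive a cerclage only after cervical shortening, so stopping is probably commoner in the pessary arm. It is not confined to that arm: section 6.1 says "The pessary or cerclage will be removed at 37+0 weeks of gestation, or before if any unexpected event occurs", and 5.3 also covers voluntary withdrawal.

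Whatever happens with 5.3 and 8.3, up to a quarter of primary outcomes are expected to be missing. A chi-square test can use only children with an outcome unless a rule says otherwise, so 9.4's promise cannot be met as written. A larger sample protects precision, not validity. Readers would have no pre-specified way to see whether the missing children could change the conclusion.

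**Working it through.** **Inputs.** From the synopsis and 9.2: 8% against 20%, two-sided 5%, 80% power, 121 evaluable and 155 recruited per arm. Loss is 25% (synopsis, 9.1) or 15% (9.2). The 8% and 20% are treated as adverse-event rates (death or disability), the only reading under which the pessary is beneficial. All p-values are from uncorrected chi-square tests.

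**1. The plan's own sample size.** The pooled formula gives n = [1.96√(2×0.14×0.86) + 0.8416√(0.08×0.92 + 0.20×0.80)]² / 0.12² = 130.1, so 131 per arm rather than 121. Power at n is Φ{[0.12 − 1.96√(2×0.14×0.86/n)] / √(0.2336/n)}:

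- n=121: 77%.
- 25% loss: 155×0.75 = 116, below the stated 121; power 75%.
- 15% loss: 155×0.85 = 131.75, about 131; power 80%.

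Also, 121/0.75 = 161.3 and 121/0.85 = 142.4, whereas 131/0.85 = 154.1, which rounds up to 155. So 155 fits 131 evaluable with 15% loss; that is an inference, since the plan does not say so.

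**2. How far the missing children can move the result.** At 25% loss, 116 are observed and 39 missing per arm. Planned rates give 9/116 against 23/116, p=0.008. Expected events among the missing are 39×0.08 + 39×0.20 = 10.9. If missing children resemble their own arm (3 and 8 events), the result is 12/155 against 31/155, p=0.002. Adding k pessary and m control events among the missing gives (9+k)/155 against (23+m)/155:

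| Missing control events | Last significant k | First non-significant k |
|---|---|---|
| 4/39 | 6/39, p=0.046 | 7/39, p=0.071 |
| 8/39 | 9/39, p=0.043 | 10/39, p=0.064 |
| 12/39 | 12/39, p=0.039 | 13/39, p=0.057 |

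In the middle row the tipping rate is 10/39 = 26%, over three times the observed pessary rate of 9/116 = 7.8%, with missing controls at 8/39 = 21%. At 15% loss (132 observed, 23 missing; 11/132 against 26/132) and 5/23 missing control events, 7/23 missing pessary events gives p=0.043 and 8/23 gives p=0.064.

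**3. Size of the 5.3/8.3 problem.** No document gives a stopping rate, so every value here is assumed: no true effect, 14% events in both arms, 25% background loss, and a quarter of stoppers' events known as deaths and always kept. Let f be the share of pessary women who stop, e their event rate and L the share of stoppers lost because follow-up ended. Non-stoppers have rate q = (0.14 − f·e)/(1 − f). The observed pessary rate is

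[0.75(1−f)q + f·e(0.25 + 0.75×0.75(1−L))] / [0.75(1−f) + f(0.25e + 0.75(1−0.25e)(1−L))], compared with 0.14. Type I errors are from 200,000 simulated trials per scenario.

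- f=10%, e=30%, L=1: q=0.122; (0.0825+0.0075)/(0.675+0.0075) = 0.132, a bias of 0.8 points towards the pessary; type I error 5.4%. With L=0.5: 0.3 points, 5.1%.
- f=5%, e=20%, L=0.5: no bias to one decimal, 5.0%.
- f=20%, e=40%, L=1: (0.045+0.020)/(0.600+0.020) = 0.105, 3.5 points, 11.7%. If controls stop at half the rate: 1.9 points, 7.0%.
- Controls stop at the same rate with the same risk: no bias.
- Stoppers at average risk (f=10%, e=14%, L=1): 0.4 points against the pessary.

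**4. Equal retention is not enough.** Assume a 14% true rate and 25% loss in both arms, but half of the pessary arm's events among the lost. The observed pessary rate is 0.07/0.75 = 9.3% against 14%. At 116 per arm the test then rejects about 20% of the time, with no true effect.

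**The case against.** The strongest defence concerns 5.3 and 8.3. Section 5.3 speaks of the women, and its wording matches the usual obstetric care described in 4.4 and 4.6. Section 8.3 reads as generic drug-trial text. Section 8.1 says of a woman with a serious adverse effect that "she will return to the standard control", which does not suggest leaving the study. Child follow-up is set separately, without a treatment condition. Most of this stands. A reader might infer that the plan excludes children of women who stop from the primary outcome, or that a serious pro-pessary bias follows. The documents do not support either: the text is ambiguous, 4.9, 7.2, 9.1 and 9.4 point to full follow-up, and the 11.7% type I error needs every assumed extreme together. What remains is that the only explicit rules for these women stop short of the primary outcome, and that no section says their children continue.

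A second objection is that the planned result is fairly robust: with missing controls near 20%, missing pessary children would need over three times the observed pessary rate to overturn it. That is true of the planned effect; a smaller observed effect would have less margin. Nor can one rely on similar retention in the two arms, because the reasons for loss may differ by arm.

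Finally, the choice of imputation model is partly a matter of preference. The essential minimum is a stated rule plus one sensitivity analysis. Imputation corrects only for missingness that its own variables explain, so the tipping-point analysis carries the rest.

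**Conclusion.** The point holds and should be fixed. It has three parts of unequal weight.

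- **No missing-data rule or sensitivity analysis for the primary outcome.** This is the main part and rests on the text alone. At the planned rates with 25% loss, p=0.008 becomes p=0.064 if 10/39 missing pessary and 8/39 missing control children have events.
- **5.3 and 8.3 against 4.9, 7.2, 9.1 and 9.4.** This is an ambiguity to reconcile, not proof of loss. The bias is under 1 point under mid-range assumptions; it could be larger, nil or slightly against the pessary. It depends on stopping rates that no document gives.
- **25% against 15% dropout.** At 25%, 155 per arm does not deliver the stated 121 evaluable, and power is about 75%; at 15% it leaves about 131 and about 80%. A reader might infer that enrolment must rise. That does not follow: the inconsistency calls for one figure and an honest statement of the power it gives.

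Confidence is medium: the textual conflicts are plain, but the practical size of the loss cannot be known from the documents.

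**What to change.** 1. **Sections 5.3 and 8.3:** reconcile them with 4.9, 7.2 and 9.4. Suggested wording: *Stopping treatment does not end study follow-up. Unless consent to follow-up is withdrawn, mother and child are followed to the 3-year assessment.* Define the end-of-study assessment in 8.3 or delete the term.
2. **Sections 9.1 and 9.4:** state that children are analysed by assigned arm, that known deaths count as events, and that the chi-square test on observed outcomes remains primary. Pre-specify a tipping-point grid over missing events in both arms. Add, as a sensitivity analysis, a small multiple imputation using arm, gestational age at birth and neonatal morbidity. With about 9 + 23 = 32 observed events expected, only a small model is supportable, which is why it should not replace the primary test.
3. **Synopsis, 9.1 and 9.2:** state one dropout figure, and restate the evaluable number and power that 155 per arm gives at that figure. No extra enrolment is needed for this.

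Cost: a sentence each in 5.3 and 8.3, a paragraph in 9.1/9.4, and a corrected sample-size statement, all using data already planned. The downsides are a little more analysis work, a few more families to contact at 3 years, and a less favourable stated power if 25% is kept.
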